## 8.2. Secondary Efficacy Endpoint and Analyses

### 8.2.1. Proportion of patients that achieve ability to walk alone at any post-Baseline visit up to 12 Months

The developmental milestone walks alone as assessed by Bayley-III Gross Motor Subtest #43 will be assessed at the scheduled visits in accord with the Schedule of Assessments. The developmental milestone achievement of each patient in the study is based on the video evidence reviewed and confirmed by an independent central reviewer, as specified in SAP Section 6.4.3. The proportion of patients  $\geq$  6 months and  $<$  24 months and the proportion of patients  $\geq$  24 and  $<$  60 months at time of dosing who achieve the ability to walk alone up to 12 months will be summarized separately. The summaries will be done by dose and overall.

For the summary of each age group, the data from the historical dataset of PNCR network will also be included by the matched age group and analysis visits. The PNCR dataset evaluated the ability to walk alone per HFMSE item #20. PNCR patients with an HFMSE item #20 score of 2 at either the Baseline visit or at any post-Baseline visit within 12 months of Baseline will be considered to have achieved the developmental milestone. The HFMSE will not be started until patients reach 24 months of age; however, the Bayley-III will be assessed at Screening and all study visits. All patients who are able to walk alone at any post-baseline visit up to Month 12 will be classified as responders. All other patients will be classified as non-responders.

The corresponding p-value from Fisher's exact test will be computed for the comparison between AVXS-101 Dose B and PNCR data for each age group. The summary and statistical analysis will be done using the ITT Set. In each age group, the actual proportions as well as the difference of the proportions between two data sources will be summarized and the exact 95% CI will be provided accordingly.

For each age group, the time to achieving ability to walk alone will be summarized for patients overall and by dose using the ITT Set. The study day will be used as the time variable. Age at baseline will be used as covariate. A Cox regression model will be used to obtain the hazard ratio with 95% CI of AVXS-101 to the data from PNCR.

All efficacy analyses stated above may also be performed using the ECAS as a sensitivity analysis in the event the ECAS contains a subset of patients of the ITT Set. Additionally, a sensitivity analysis will be performed for patients aged  $\geq$  24 and  $<$  60 months at time of dosing using the Sensitivity PNCR group. This sensitivity analysis will be based on the ITT Set and separately using the ECAS in the event the ECAS contains a subset of patients of the ITT Set.

If necessary, an additional set of sensitivity analyses may be conducted to include patients in the  $\geq$  6 months and  $<$  24 months group who demonstrated the developmental milestone of walking alone which occurred after but within 3 months of the upper bound of the Month 12 visit window (day 374) due to COVID-19 disruptions.

In the first sensitivity analysis, the proportion of patients that achieve the developmental milestone at any post-baseline visit (considering the expanded 3-month window) will be summarized overall and by dose. The corresponding p-value from a Fisher's exact test will be

computed for the comparison between AVXS-101 Dose B and PNCR data. The summary and statistical analysis will be conducted using the ITT Set. The difference in the proportions between AVXS-101 and PNCR will be summarized and the exact 95% CIs will be provided accordingly.

In the second sensitivity analysis, the time from dosing to achieving the ability to walk alone will be summarized for patients overall and by dose in the ITT Set. The study day will be used as the time variable. Age at baseline will be used as a covariate. The probability of the ability to walk alone over time will be estimated using Kaplan-Meier methods. A Cox regression model will be used to obtain the hazard ratio with 95% CI for AVXS-101 Dose B and PNCR. In this analysis, patients who demonstrated the milestone within the expanded 3-month window after Month 12 will be censored at the last attended visit prior to when the Month 12 visit was scheduled to occur.

Final

#### 8.4. Sensitivity Analysis of the Primary Endpoint

The primary analyses described in the SAP Section 8.1.1 and Section 8.1.2 may be conducted on the ECAS as a sensitivity analysis, in the event that the ECAS contains a subset of patients of the ITT Set.

The primary and secondary analyses for patients aged  $\geq 24$  and  $< 60$  months at time of dosing will be conducted on the Sensitivity PNCR group as a sensitivity analysis.

#### **8.4.1. Proportion of patients with a $\geq 3$ -point increase from baseline in HFMSE score among patients $\geq 24$ months and $< 60$ months of age at time of dosing**

The proportion of patients that achieve  $\geq 3$ -point increase from baseline in HFMSE score at any post-baseline visit up to 12 months will be summarized overall and by dose. The proportion of patients achieving a  $\geq 3$ -point increase from baseline in HFMSE within 12 months of their baseline visit in the historical dataset of PNCR network will also be summarized.

The corresponding p-value from Fisher's exact test will be computed for the comparison between AVXS-101 Dose B and PNCR data. The difference between the proportions between AVXS-101 and PNCR will be summarized and the exact 95% CIs will be provided. The summary and statistical analysis will be conducted using the ITT Set and repeated for the ECAS, in the event the ECAS contains a subset of patients of the ITT Set, for both the Primary PNCR and Sensitivity PNCR groups.

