## 5.6. PNCR Population-Matched Control Population

A population-matched control cohort will be drawn from the PNCR Natural History dataset. The PNCR is a large natural history study developed from a cohort of 337 patients with any form of spinal muscular atrophy followed at 3 large, internationally recognized tertiary medical centers with significant expertise in the management of SMA (Harvard University/Boston Children's Hospital, Columbia University and the University of Pennsylvania/Children's Hospital of Philadelphia).

Previously identified patients with any form of SMA, of any age, followed in PNCR site clinics and newly diagnosed patients were enrolled. All eligible patients were offered participation. Study visits were scheduled at baseline and at 2, 4, 6, 9, and 12 months and every 6 months thereafter. The SMA standard of care guidelines published in 2007 were used as a basis for providing uniform care among the study sites.

For purposes of this study, sitting (for SMA-II) was defined as being able to sit independently for > 10 seconds, and walking alone was defined as having scored 2 points on item #20 of the HFMSE at any time. All patients with SMA type 2 or 3 who provided sufficient records and follow-up for evaluation and met the basic entry criteria for the two cohorts of the AVXS-101-CL-102 study (3 copies of *SMN2*, symptom onset before 12 months of age and baseline and follow-up visits within the age criteria for the study) were considered for possible inclusion in the natural history comparison dataset. The *SMN2* modifier mutation (c.859G>C) described by Prior and colleagues (Prior et al., 2009) was not assessed in the PNCR study cohort.

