**Table 3: Developmental Milestone Checklist**

Developmental Milestone- Bayley Scales Item Number	Performance Criteria
Head Control – Gross Motor Subtest Item #4	Child holds head erect for at least 3 seconds without support
Rolls from Back to Sides – Gross Motor Subtest Item #20	Child turns from back to both right and left sides
Sits Without Support – Gross Motor Subtest Item #26	Child sits alone without support for at least 30 seconds
Stands With Assistance - Gross Motor Subtest Item #33	Child supports own weight for at least 2 seconds
Crawls – Gross Motor Subtest Item #34	Child makes forward progress of at least 5 feet by crawling on hands and knees
Pulls to Stand – Gross Motor Subtest Item #35	Child raises self to standing position using chair or other convenient object for support
Walks With Assistance – Gross Motor Subtest Item #37	Child walks by making coordinated, alternated stepping movements
Stands Alone – Gross Motor Subtest Item #40	Child stands alone for at least 3 seconds after you release his or her hands
Walks Alone – Gross Motor Subtest Item #43	Child takes at least five steps independently, displaying coordination and balance

The primary efficacy endpoint for the patients  $\geq$  6 months and  $<$  24 months at time of dosing is the proportion of patients achieving the ability to stand alone. The ability to stand alone will be evaluated by the CE using the Bayley-III – Gross Motor Subtest # 40 at visits specified by the Schedule of Assessments. Patients who achieve standing alone at any post-procedure visit up to 12 months will be classified as responders. Otherwise, the patient will be classified as a non-responder.

The HFMSE was devised for use in children with SMA Type 2 and Type 3, age 24 months and above, to give objective information on motor ability and clinical progression. The HFMSE will be administered by a CE in accord with the Protocol Schedule of Assessments within 30 days of dosing and monthly through twelve (12) months for all patients  $\geq$  24 months of age. The primary efficacy endpoint for the patients  $\geq$  24 months and  $<$  60 months at time of dosing is the change from baseline in HFMSE. The change from baseline to the 12-month study visit will be calculated.

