#### 6.5. Visit Windows

The time windows specified in Table 4.1 (Cohort 1 and 2) and Table 4.2 (Cohort 3) define how efficacy data will be assigned to protocol-specified time points. All time points and corresponding time windows are defined based on dosing date.

If more than one efficacy observation for a specific assessment is included in a time window, the assessment closer to the nominal time will be used. If there are two efficacy observations

equally distant to the nominal time, the latest one will be used in analyses. Any efficacy assessments occurring outside the analysis windows will be considered an assessment of an unscheduled visit.

**Table 4.1: Analysis Time Windows of Bayley Scales, HFMSE, Development Milestones and Pulmonary Exam – Cohort 1 and 2 Patients**

Scheduled Visit	Nominal Days (Study Day)	Acceptable Analysis Window in Study Days (Min Day – Max Day)
Baseline	-	< 1
Month 1	30	1 to 44
Month 2	60	45 to 74
Month 3	90	75 to 104
Month 4	120	105 to 134
Month 5	150	135 to 164
Month 6	180	165 to 194
Month 7	210	195 to 224
Month 8	240	225 to 254
Month 9	270	255 to 284
Month 10	300	285 to 314
Month 11	330	315 to 344
Month 12	360	≥345

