**Table 5: Analysis Time Windows for dataset from PNCR Network**

Scheduled Visit	PNCR
Baseline	Visit Month 0
Month 2	Visit Month 2
Month 4	Visit Month 4
Month 6	Visit Month 6
Month 9	Visit Month 9
Month 12	Visit Month 12

If a PNCR patient is missing efficacy data at Baseline, then the earliest non-missing assessment collected post-Baseline will be re-mapped and considered their Baseline value, and subsequent visits occurring within 12 months after the re-mapped Baseline value will be included in the analysis.

For example, if a PNCR patient is missing their HFMSE assessment at Visit Month 0 and Visit Month 2 and their first non-missing HFMSE assessment occurred at Month 4, then their data would be re-mapped as follows:

- Visit Month 4 assessment is considered Baseline
- Month 6 is re-mapped as Month 2 (visit occurred 2 months after Baseline)
- Month 9 is remapped as Month 5 (visit occurred 5 months after Baseline)
- Month 12 is remapped as Month 8 (visit occurred 8 months after Baseline)
- Next available visit is >12 months after Baseline so it is not considered

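### SAP 8.4.1's any-visit responder rule gives treated children up to 12 looks and PNCR controls at most five, so its Fisher test and interval lean towards AVXS-101 by an amount the documents do not fix

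*SAP*

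**What the plan says.** SAP 8.4.1 sits under the heading for sensitivity analyses of the primary endpoint and concerns patients aged 24 to under 60 months at dosing. A treated patient responds on an HFMSE gain of at least 3 points "at any post-baseline visit up to 12 months will be summarized overall and by dose". For controls, the proportion with such a gain "within 12 months of their baseline visit in the historical dataset of PNCR network will also be summarized". A p-value from Fisher's "exact test will be computed for the comparison between AVXS-101 Dose B and PNCR data", with an exact 95% interval for the difference, against both the Primary and the Sensitivity PNCR groups.

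The assessment schedules differ:

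- **Treated.** SAP 6.4.3 has HFMSE given "within 30 days of dosing and monthly through twelve (12) months for all patients" aged 24 months or more. Table 4.1 has 12 post-baseline windows, and the Month 12 window has no upper limit (day 345 onward).
- **PNCR.** SAP 5.6: "Study visits were scheduled at baseline and at 2, 4, 6, 9, and 12 months and every 6 months thereafter". Table 5 has five post-baseline rows: Months 2, 4, 6, 9 and 12.

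Sections 8.1.2 and 8.2.1 bring PNCR data in by matched analysis visits. Section 8.4.1 does not. It also asks for no confirmation of the gain and makes no allowance for the number of assessments. SAP 6.1 sets two-sided alpha at 0.05 with no multiplicity adjustment.

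**The concern.** The rule depends on the largest change seen over all available visits. HFMSE varies from visit to visit, so the largest of 12 changes tends to exceed the largest of five even when the underlying courses are identical. The listed PNCR months are a subset of the treated months, so for the same true course the treated maximum can only be equal or higher.

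Five is a ceiling for controls. The SAP 6.5 re-mapping example leaves a control with three looks (Months 2, 5 and 8). A control whose HFMSE baseline falls after the first PNCR year is seen only every six months and has about two looks. SAP 5.6.1 allows the Primary PNCR follow-up evaluation at 12 to 14 months, which can fall outside a 12-month limit. SAP 5.6.2 says some Sensitivity PNCR patients lack a full 12 months of data.

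The analysis is placed as a check on the primary result. A check that tilts towards the drug is weak support, and the estimated difference and its interval are shifted even when the p-value is not significant.

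**Working it through.** **1. The plan's own figure.** SAP 3.7 claims over 90% power for the older-group HFMSE comparison; it gives no operating figure for the responder test. The inputs are expected changes of +8 and -1.13 (difference 9.13), SD 4.90, and 12 versus 15 patients. The noncentrality is 9.13 / (4.90 × √(1/12 + 1/15)) = 9.13 / 1.898 = 4.81 on 25 degrees of freedom. Two-sided power at 0.05 is 99.6%, so the claim is met.

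**2. Model with no treatment effect.** In both groups, the change at month m = (−1.13 + random slope) × m/12 + e(m) − e(0), rounded to whole points. The visit error e has SD σ. The 12-month SD is held at 4.90, so with independent errors the slope SD is √(4.90² − 2σ²); for σ = 2 this is √(24.01 − 8) = 4.00. The largest possible σ is 4.90/√2 = 3.46. **σ is not in the documents and is assumed.** A responder has a maximum change of at least 3 over the visits looked at.

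Check at a single look: P(change at Month 12 ≥ 2.5 before rounding) = 1 − Φ((2.5 + 1.13)/4.90) = 1 − Φ(0.741) = 23%. The simulation also gives 23%.

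**3. False-positive rate.** The binomial probabilities of all tables with two-sided Fisher p ≤ 0.05 and a higher treated proportion are summed. The nominal rate is 2.5% per side.

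| Assumed σ (independent errors) | Null responders, 12 looks | Null responders, 5 looks | Favouring AVXS-101, 12 vs 15 | Favouring AVXS-101, 12 vs 17 |
|---|---|---|---|---|
| 1 | 33% | 28% | 2.4% | 3.5% |
| 1.5 | 46% | 36% | 4.2% | 5.7% |
| 2 | 57% | 44% | 5.8% | 6.2% |
| 2.5 | 64% | 50% | 7.6% | 6.5% |

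At σ = 0.5 the gap in responder rates is only about 1.5 percentage points.

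**4. Correlated visit errors (also assumed).** With first-order autoregressive errors, 12 versus 15 patients and σ = 1, 1.5, 2 and 2.5, the favourable rate is:

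- monthly correlation 0.5: 1.8%, 2.8%, 3.8%, 4.9%;
- monthly correlation 0.8: 1.4%, 1.8%, 2.2%, 2.7%.

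**5. Look counts.** The HFMSE row of the Schedule of Assessments has no mark at Day 60, so a strict reading gives 11 treated looks. At σ = 2 with independent errors the null rates are then 54% versus 44%. A control re-mapped to three looks has a null rate of 35%.

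**6. Candidate remedies.** If both groups truly had the same five visits, null rates would be equal and the favourable error about 1.1% to 1.5% (12 versus 15). If treated patients were cut to five looks but every control had only two, the error would still be about 6.4% at σ = 2. With Month 12 only, each group has one look and a 23% null rate.

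**The case against.** The asymmetry and its sign are not in dispute. The case on the other side concerns size, remedy and reach, and most of it stands.

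- **Benchmark.** The SAP's level is 2.5% per side. Fisher's test is conservative at these sample sizes, so setting the rates against the roughly 1.2% seen with matched visits overstates the harm. At σ = 1 (12 versus 15) there is no excess over 2.5%. Total two-sided rejection at σ = 1, 1.5, 2 and 2.5 is 3.3%, 4.6%, 6.0% and 7.7%, within 5% in two of the four settings.
- **Independence.** Monthly scores in one child may share persistent deviations, so 12 looks need not be 12 independent chances. At a correlation of 0.8 the error is essentially nominal.
- **Remedy.** Restricting treated patients to Months 2, 4, 6, 9 and 12 looks like the obvious repair, but it equalises looks only if every control has all five visits.
- **Reach.** This is one supportive analysis in a Phase 1 study.

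A reader might infer that the error rate of this test is known to be materially inflated. The documents do not support that, because they supply neither σ nor the correlation. A reader might also infer that the primary HFMSE result shares the flaw. It does not: the MMRM in 8.1.2 estimates the contrast at Month 12, not a best-of-visits value. The weighted-mean analysis in 8.4.2 averages visits, so it has no maximum-over-looks bias either.

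None of this removes the shift in the estimated difference or supplies the visit matching that 8.4.1 lacks.

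**Conclusion.** The point holds. The comparison in 8.4.1 is biased towards AVXS-101, because up to 12 treated looks (or 11) are set against at most five control looks, sometimes two or three. The direction follows from the schedules alone, for patients with the same true course.

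The size is open. Over the assumed range, the favourable false-positive rate runs from 1.4% (correlation 0.8, σ = 1) to 7.6% (independent errors, σ = 2.5) against 2.5%, with 12 versus 15 patients and 12 versus five looks. These figures assume linear patient courses, normal errors, a 12-month SD of 4.90 and complete visits. Fewer control looks would widen the gap. The change should be made, but nothing here undermines the primary analysis.

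**What to change.** In SAP 8.4.1, base the Fisher test and the exact interval on a gain of at least 3 points **at Month 12 in both groups**:

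- for Primary PNCR, use the 12 to 14 month evaluation;
- for treated patients, use a comparable Month 12 window with an upper bound, since Table 4.1 leaves it open;
- for Sensitivity PNCR, include only controls with a Month 12 score.

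Alternatively, match treated looks to the visit months each control actually has, not to a fixed set of five. Either way, report the any-visit rates descriptively, without a p-value.

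**Cost.** The data are already collected, so the programming is small. The treated responder rate may fall. Power need not suffer much: with the SAP's expected +8 points, 12 versus 15 patients and independent errors, the Month 12 rule has about 92% power at every σ tried from 0.5 to 3. The any-visit rule has 94%, 89% and 85% at σ = 1, 2 and 2.5, helped by its bias. Five shared visits would give 91%, 80% and 73%. Restricting Sensitivity PNCR to controls with a Month 12 score will reduce that group by a number the documents do not give.

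SAP 2.2.2 says efficacy was already analysed when the last Cohort 2 patient completed Month 12, and SAP 19.3 shows that 8.4.1 dates from version 5.0. The change should therefore be dated, labelled post hoc and shown beside the pre-specified result.

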#### **8.4.2. Change from Baseline in HFMSE across all available assessments (Months 1-12) among patients $\geq 24$ months and $< 60$ months of age at time of dosing**

The HFMSE total score at baseline and the weighted mean change from baseline in HFMSE total score considering all post-baseline visits through Month 12 will be summarized for patients overall and by dose. All change from baseline HFMSE scores across all available post-baseline visits (Months 1-12) will be averaged together for this measure and summarized. The number of available post-baseline HFMSE scores available for each patient will be used as the weight for this calculation. For the PNCR patients, the weighted mean change from baseline in HFMSE total score recorded across all visits through 12 months after the patient's baseline assessment will be summarized. The number of available post-baseline HFMSE scores available for each patient will be used as the weight for this calculation. For patients where only a single post-baseline HFMSE score is available, the single value will be used.

The scores will be analyzed using an Analysis of Covariance (ANCOVA) model which will include the weighted mean change from baseline HFMSE score as the dependent variable, fixed effect of cohort (AVXS-101 and PNCR), and baseline HFMSE score and age at baseline as covariates. The unadjusted means, LS means, differences between LS means, a 95% 2-sided CIs for each difference and the p-values from model effects will be reported.

This analysis will be repeated in the subset of patients that achieve  $\geq 3$ -point increase from baseline in HFMSE and separately in the subset of patients that achieve a  $< 3$ -point increase from baseline in HFMSE, defined as follows:

- AVXS-101 treated patients with a weighted mean change from baseline in HFMSE total score of  $\geq 3$  points considering all available post-baseline visits through Month 12
- AVXS-101 treated patients with a weighted mean change from baseline in HFMSE total score of  $< 3$  points considering all available post-baseline visits through Month 12
- PNCR patients with a weighted mean change from baseline in HFMSE total score of  $\geq 3$  points considering all available HFMSE scores recorded across all visits through 12 months after the patient's baseline assessment

- PNCR patients with a weighted mean change from baseline in HFMSE total score of <3 points considering all available HFMSE scores recorded across all visits through 12 months after the patient's baseline assessment

The summary and statistical analysis will be conducted using the ITT Set and repeated for the ECAS, in the event the ECAS contains a subset of patients of the ITT Set, using both the Primary PNCR and Sensitivity PNCR groups.

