#### 2.2.2. Additional Safety and Efficacy Analysis

An additional analysis of efficacy and safety data was conducted once the last Cohort 2 patient completed the 12 month visit.

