#### **8.1.2. Change from Baseline in HFMSE at the 12 Month study visit for patients $\geq$ 24 months and $<$ 60 months of age at time of dosing**

The baseline, post-baseline, and change from baseline values in HFMSE will be summarized for patients overall and by dose. The summary and primary statistical analysis will be conducted using the ITT Set, and will be repeated using the PP Set as a sensitivity analysis. The patient data from the Primary PNCR group will also be included in the descriptive summary and analyses by the matched age group and analysis visits. The change from baseline to 12-month visit will be analyzed using a mixed model with repeated measurement (MMRM). The model will include the change from baseline as the dependent variable, fixed effect of cohort (AVXS-101 and PNCR), visit, and covariates of baseline HFMSE and age at baseline, and interactions of cohort\*age at baseline, baseline HFMSE\*visit, baseline HFMSE\*cohort, and cohort\*visit. A compound symmetry covariance structure will be assumed initially to model the within-patient errors; however, if compound symmetry results non-convergence, the variance component will be used. The unadjusted means, least squares (LS) means, differences between LS means, a 95% 2-sided CIs for each difference and the p-values from model effects will be reported for each scheduled visit.

A sensitivity analysis may be performed using the ECAS, in the event the ECAS contains a subset of patients of the ITT Set.

A sensitivity analysis will also be performed using the Sensitivity PNCR group and will be based on the ITT Set. This analysis may be repeated using the ECAS, in the event the ECAS contains a subset of patients of the ITT Set.

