#### **8.4.3. Change from Baseline in HFMSE across all available assessments (Months 1-6 vs. Months 7-12) among patients $\geq 24$ months and $< 60$ months of age at time of dosing**

The weighted mean change from baseline in HFMSE total score considering all post-baseline visits from Months 1 through 6 and separately considering all post-baseline visits from Months 7 through 12 will be summarized for patients overall and by dose. All change from baseline HFMSE scores available across all post-baseline visits during the first 6 months of the trial (Months 1-6) will be averaged together for one measure, and all change from baseline HFMSE scores available across all post-baseline visits during the last 6 months of the trial (Months 7-12) will be averaged together for the second measure. The number of available post-baseline HFMSE scores available for each patient within each window (Months 1-6, Months 7-12) will be used as the weight for this calculation.

The difference between scores (Months 1-6 vs. Months 7-12) will be analyzed using an ANCOVA model which will include the weighted mean change from baseline HFMSE score as the dependent variable, time period (Months 1-6, Months 7-12), and baseline HFMSE score and age at baseline as covariates. The unadjusted means, LS means, differences between LS means, a 95% 2-sided CIs for each difference and the p-values from model effects will be reported.

This analysis will be repeated in the subset of subset of patients that achieve a  $\geq 3$ -point increase from baseline in HFMSE (Months 1-6 vs. Months 7-12) and separately in the subset of subset of patients that achieve a <3-point increase from baseline in HFMSE (Months 1-6 vs. Months 7-12), defined as follows:

- AVXS-101 treated patients with a weighted mean change from baseline in HFMSE total score of  $\geq 3$  points considering all post-baseline visits from Months 1 through 6
- AVXS-101 treated patients with a weighted mean change from baseline in HFMSE total score of <3 points considering all post-baseline visits from Months 1 through 6
- AVXS-101 treated patients with a weighted mean change from baseline in HFMSE total score of  $\geq 3$  points considering all post-baseline visits from Months 7 through 12
- AVXS-101 treated patients with a weighted mean change from baseline in HFMSE total score of <3 points considering all post-baseline visits from Months 7 through 12

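### SAP 8.4.2 and 8.4.3 test inside HFMSE subsets cut on the analysed outcome, and 8.4.3 compares two half-years in the same children with no within-child term

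*SAP*

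**What the plan says.** All of this concerns the older age group and sits under SAP 8.4, the sensitivity analyses of the primary endpoint.

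**SAP 8.4.2.** Each child's HFMSE changes over Months 1-12 are averaged. An ANCOVA with cohort, baseline HFMSE and age gives LS-mean differences, 95% intervals and p-values. The section continues: "This analysis will be repeated in the subset of patients that achieve" at least 3 points, with a separate repeat below 3. The subset definitions use the same averaged change in both cohorts, for example "PNCR patients with a weighted mean change from baseline in HFMSE total score of <3 points considering all available HFMSE scores". The work is done against both PNCR comparator groups.

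**SAP 8.4.3.** Each treated child supplies a Months 1-6 average and a Months 7-12 average. "The difference between scores (Months 1-6 vs. Months 7-12) will be analyzed using an ANCOVA model which will include the weighted mean change from baseline"; the terms are "time period (Months 1-6, Months 7-12), and baseline HFMSE score and age at baseline as covariates". No patient effect, pairing or covariance structure is named. On weighting, the number of scores "available for each patient within each window (Months 1-6, Months 7-12) will be used as the weight for this calculation". The model is then repeated in subsets of at least 3 and below 3 points, defined separately within each period.

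**Elsewhere.** The primary MMRM in SAP 8.1.2 does handle dependence within a child: "A compound symmetry covariance structure will be assumed initially to model the within-patient errors". SAP 8.4.1 compares a related but different proportion, in which a child counts on reaching a 3-point "increase from baseline in HFMSE score at any post-baseline visit up to 12 months will be summarized overall and by dose". SAP 2.2.2 records: "An additional analysis of efficacy and safety data was conducted once the last Cohort 2 patient completed the 12 month visit".

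**The concern.** There are three separate faults.

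1. **8.4.2 subsets.** Selecting children on the outcome and then comparing that outcome between cohorts truncates both distributions at the same point. What remains reflects the shape of the two tails. A large real effect can look like little or none among responders and non-responders alike, in cells of a few children, yet an interval and p-value are planned.
2. **8.4.3, all patients.** Two rows per child enter the model as if they came from different children. If a child's two averages are positively correlated after adjustment, the variation between children stays in the error term although it cancels from the contrast. A real change between half-years could be missed.
3. **8.4.3 subsets.** A child can be below 3 points early and above it late. The early and late groups are then not the same children, and the contrast mixes change over time with change of membership.

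**Working it through.** **Inputs.** SAP 3.7: expected treated change +8, PNCR change -1.13, SD 4.90 in both, 12 treated children on Dose B. SAP 5.6.1: 15 PNCR children. SAP 6.1: two-sided alpha 0.05. Three inputs are assumed because the documents do not give them: that these Month-12 values carry over to period averages, the within-child correlation, and how much the covariates explain.

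**The plan's own figure.** SAP 3.7 states power above 90%. For a two-sample t-test the noncentrality is 9.13 / (4.90 × √(1/12 + 1/15)) = 9.13 / 1.898 = 4.81 on 25 df, which gives 99.6%. The stated figure holds. No power is stated for 8.4.2 or 8.4.3.

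**8.4.2 subsets.** For a normal outcome with mean μ and SD σ, put a = (3 − μ)/σ. The mean at or above the cut is μ + σφ(a)/(1 − Φ(a)); the mean below it is μ − σφ(a)/Φ(a).

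- Treated, a = (3 − 8)/4.90 = −1.02: means 9.37 and 0.45.
- PNCR, a = (3 + 1.13)/4.90 = 0.84: means 5.73 and −2.84.
- Differences: 9.37 − 5.73 = 3.64, and 0.45 + 2.84 = 3.29, against 9.13 overall.

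Children improving gradually would average less than +8 over the year, so the treated mean is varied. Probabilities are binomial, with 12 treated and 15 PNCR children.

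| Assumed treated mean | 3 | 4.3 | 6 | 8 |
|---|---|---|---|---|
| Difference, all children | 4.13 | 5.43 | 7.13 | 9.13 |
| Difference, at least 3 | 1.18 | 1.69 | 2.49 | 3.64 |
| Difference, below 3 | 1.93 | 2.37 | 2.84 | 3.29 |
| Expected n, at least 3 (treated / PNCR) | 6.0 / 3.0 | 7.3 / 3.0 | 8.8 / 3.0 | 10.2 / 3.0 |
| Expected n, below 3 (treated / PNCR) | 6.0 / 12.0 | 4.7 / 12.0 | 3.2 / 12.0 | 1.8 / 12.0 |
| Chance some subset arm has 0 or 1 child | 17% | 19% | 27% | 53% |
| Chance no treated child is below 3 | 0.02% | 0.2% | 2.3% | 13% |

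In simulation at a treated mean of 8, with uninformative covariates, the all-patient ANCOVA reached p < 0.05 in 99% of trials. The subset ANCOVAs did so in 19% (at least 3) and 10% (below 3) of the trials where they could be fitted.

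**8.4.3, all patients, balanced visits.** Let ρ be the within-child correlation and R the share of between-child variance that baseline HFMSE and age explain. With n = 12:

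- paired SE = σ√(2(1 − ρ)/n)
- ANCOVA SE ≈ σ√(2(1 − ρR)/n)
- ratio ≈ √((1 − ρR)/(1 − ρ))

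At ρ = 0.7 and R = 0 this is 4.90 × √(2/12) = 2.00 against 4.90 × √(0.6/12) = 1.10, a ratio of 1.83. At 12 children the simulated ratios differ slightly from the formula:

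| ρ | R = 0 | R = 50% | R = 80% |
|---|---|---|---|
| 0.3 | 1.19 | 1.10 | 1.05 |
| 0.5 | 1.39 | 1.22 | 1.10 |
| 0.7 | 1.77 | 1.44 | 1.20 |
| 0.9 | 3.01 | 2.25 | 1.63 |

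For an assumed 3-point change at ρ = 0.7, power is 24%, 43% and 61% for R = 0, 50% and 80%, against 70% paired. Type I error there is 0.3%, 0.9% and 2.1%; at ρ = 0 it is 5.1%.

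**8.4.3 subsets.** The truncated means above apply again with SD 4.90. If the period means are 3 then 6, the true gain of 3 appears as 8.22 − 6.91 = 1.31 (at least 3) and 0.00 + 0.91 = 0.91 (below 3). If they are 5 then 8, it appears as 9.37 − 7.73 = 1.64 and 0.45 + 0.27 = 0.72. For ρ from 0.3 to 0.9, between 2.4 and 5.0 of 12 children change subset across these two cases.

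**The case against.** - **These are sensitivity analyses only.** True. The primary MMRM, 8.4.1 and the all-patient 8.4.2 ANCOVA are untouched. The MMRM also reports LS means by visit, so the early and late course is partly visible with dependence modelled, though without a half-year contrast. This limits the weight of the point but does not make the subset p-values meaningful.
- **A reader might infer false positives.** The cut alone does not produce them. With identical distributions in both cohorts (mean 0), the subset tests rejected in 4.8% and 5.6% of simulated trials. Spurious differences need unequal spreads, and SAP 3.7 assumes equal variance. In 8.4.3, ignoring positive correlation makes the test conservative.
- **A reader might infer that the 8.4.3 estimate is biased by uneven visit counts.** That needs the counts to be regression weights. The text attaches them to the averaging step, and the model sentence lists no weight. In an assumed case where the lower-scoring half has 2 of 6 late visits, a weighted ANCOVA was off by about 0.2 to 1.5 points, while an unweighted one had an offset near zero. The SAP leaves the reading open, so bias is not established.
- **A reader might take the 53% cell figure as the expectation.** It holds only if the Month-12 gain of 8 applies to the year's average. At treated means of 3 to 6 the chance is 17% to 27%.
- **Changing a conservative test after data were seen is itself a risk.** This stands. It is why one analysis should be named and the planned output kept beside it.

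**Conclusion.** The point holds for all three faults, in sensitivity analyses only.

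The 8.4.2 subset contrasts do not estimate a treatment effect. For assumed treated means of 3 to 8, true differences of 4.1 to 9.1 points appear as 1.2 to 3.6 (at least 3) and 1.9 to 3.3 (below 3). The 8.4.3 subset contrasts do not estimate a period effect.

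The all-patient 8.4.3 comparison is inefficient and remains interpretable: unbiased without regression weights, conservative under positive residual correlation, with a standard error about 1.05 to 3.0 times the paired one over the correlations and covariate strengths examined. It would be too strong to call that output invalid, and nothing here bears on the trial's primary or secondary results.

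The faults follow directly from the SAP text. The sizes rest on approximate normality and on inputs the documents do not give. The change is worth making, but no main conclusion depends on it.

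**What to change.** 1. Present the subsets of at least 3 and below 3 points in 8.4.2 and 8.4.3 descriptively, without intervals or p-values for differences. SAP 8.4.1 is not a substitute, because it counts a gain at any visit and not the averaged change.
2. For the all-patient 8.4.3 comparison, specify one within-child analysis: the unweighted paired difference, each child's Months 7-12 mean minus the Months 1-6 mean.
3. Record it as added after the Cohort 2 analysis in SAP 2.2.2. Keep the planned ANCOVA output beside it, noted as conservative because it ignores within-child correlation.
4. If subset outputs already exist, label those, and only those, as not interpretable as treatment or period effects.

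The cost is SAP wording and minor reprogramming, with no new data. Some planned subset p-values are lost. The paired difference gives up the visit-count weights, and a child with no score in one half-year does not contribute to it.
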